1. To evaluate at 0 – 6 and 12 months after surgery the enteric mal-absorption profile in terms of lipid (Triglycerides, cholesterol, HDL and LDL), proteins (hemoglobin, albumin and ferritin), carbohydrates and micronutrients (minerals and vitamins) and nutritional status in subjects undergoing MGB vs RYGB.
2. To compare the effect of RYGB vs MGB surgery on total weight loss percent, excess weight loss percent (%EWL), excess BMI loss percent, major co-morbidities control and quality of life.
3. To evaluate the endoscopic /histological esophageal mucosal lesions secondary to bile reflux at 12 months in MGB vs RYGB patients
4. to evaluate energy expenditure at 0 and 12 months by Indirect calorimetry

Type of study:

Multicentric Prospective pilot comparative study.

Patients:

We had to evaluate Sample Size using bariatric patients population who underwent MGB or RYGB during 12 months (the follow up period of this study) in the three centres involved in the study, because of there aren't others high methodological level studies or randomized trials or methnalysis about this argument (Primary end points and secondary and points). Our population is 285 patients: to obtain a confidence level of 95 %, an effect size of 0.5, Sample size is 90 patients (45 MGB and 45 RYGB) with an interval confidence of 8.56.

Determine Sample Size

Confidence Level: 95% 99%

Confidence Interval:

Population:

Sample size needed:

Find Confidence Interval

Confidence Level: 95% 99%

Sample Size:

Population:

Percentage:

Confidence Interval:

Tab 1

Tab 2

The sample size will be 90 cases (45 MGB and 45 RYGB) considering at least 20% drop-out at 1 year. (Tab 1-2)

Inclusion Criteria:

Obese patients with age 18-65 years old, BMI 40-55 kg/m², non smokers, and candidates to primary MGB or RYGB without any concomitant surgeries except

hiatal hernia repair. Patients will be informed on the differences of the two procedures and the enrollment in the two study groups will be on the basis of patient choice.

Exclusion Criteria:

- Age ≤ 18 or ≥ 65 years old,
- BMI ≤ 40 or ≥ 55
- Smokers
- Any required associated surgical procedure except hiatal hernia repair
- Conversion to open surgery
- Postoperative complications requiring reoperation
- No compliance to the follow up schedule.
- Histological positivity to *Helicobacter pylori* previous or current
- Patients with different intraoperative measurement of the bowel distal to Treitz Ligament (tolerance plus or minus 10%).

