Pureed lean beef, chicken or turkey, fish (or baby food meats): 80g	
Pureed fruits (or baby food fruit): 100g	
Soft cheese: 50g	
Extra virgin oil: 10g	

3. Soft Solid Proteic Diet (for 2 weeks)

Types of food	Calories/day

Reduced fat milk Lactose-free: 200ml
 
Light white yogurt: 125ml
 
Oral protein supplementation: 400ml
 
Chopped lean meats (or Lean ground beef or turkey, or Deli-sliced turkey, breast, chicken, ham): 50g
 
Tuna fish, salmon or white fish: 50g
 
Pureed fruits (or baby food fruit) or canned fruits: 100g
 
Mashed or well-cooked vegetables: 100g
 
Extra virgin oil: 10g
	
Protein: 74.4g (30.41%)
 
Fat: 32.66g (30.04%)
 
Carbohydrate: 99.4g (40.60%)
 
Kcal: 978.65

4. Maintenance (Regular Food)

Types of food	Calories/day
---------------	--------------

Reduced fat milk Lactose-free: 200ml	Protein 78.9gm (27.69%)
Biscuits: 30g	Fat 42.24gm (33.35%)
Oral protein supplementation: 200ml	Carbohydrate: 116.6 gm
Light white yogurt: 125ml	(40.9%)
Lean red meat (or tender chicken, turkey and beef: 70g	Kcal 1116.64
Fish: 70g	
Raw fruits without skins: 100g	
Raw and cooked vegetables: 100g	
Toasted breads or Low fat crackers: 30g	
Extra virgin oil: 20g	

Postoperative follow up:

Total weight loss percent, excess weight loss percent (%EWL), excess BMI loss percent, co-morbidities control and quality of life, evaluated by The TSD-OC (SIO obesity-related disability) test (19). It is a questionnaire developed by the Italian Society of Obesity (SIO); it is made of 36 items divided into 7 sections: pain, rigidity, activities of daily living, housework, outdoor activities, occupational activities, and social life. Each question is answered using a visual

analogue scale, with a score ranging from 0 (absence of difficulty) to 10 (the highest degree of disability) for each item.

Data recording and variables analysis:

Basic demographic data are recorded as well as detailed information on history, preoperative data, surgical procedure, intra-operative findings, and postoperative course. The statistical analysis will be performed on the pooled groups. All statistical analyses will be performed using IBM SPSS v.20 software. P value of less than 0.05 will be considered statistically significant.

References

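### The stated confidence interval of 8.56 holds only if all 90 patients are analysed; after the protocol's own 20% drop-out the margin is 10.0 at best

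*Protocol*

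**What the plan says.** The sample size is set in the Patients section of the protocol. The source population is the bariatric patients operated on in the three centres over 12 months: "Our population is 285 patients". The inputs named are a 95% confidence level and "an effect size of 0.5". The result reads: "Sample size is 90 patients (45 MGB and 45 RYGB) with an interval confidence of 8.56". The field labels of two calculator screens follow, one that determines a sample size and one that finds a confidence interval; their values are not readable in the text at hand. The section then closes with: "The sample size will be 90 cases (45 MGB and 45 RYGB) considering at least 20% drop-out at 1 year", and refers to both tables.

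The text gives no separate evaluable number and no power. The Primary end point section places the main comparison at 6 and 12 months, and the secondary end point is measured before surgery and at 12 months.

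**The concern.** One number, 90, carries two statements. In the first it is the number of patients that yields a precision of 8.56. In the second it is a number that already absorbs a loss of at least one patient in five by 1 year. If the second statement is right, 90 patients will not be there at 12 months, and a precision calculated on 90 does not describe the data that will be analysed then.

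What is at stake is limited but concrete. The 8.56 is the only precision figure in the protocol, and a reader will take it as what the study is planned to deliver. The end points are assessed at a time when the protocol itself expects drop-out. The exclusion criteria also list conversion to open surgery, reoperation for complications and non-compliance with follow-up. All of these arise after enrolment and could reduce the evaluable set further.

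**Working it through.** **Inputs, all from the Patients section.** Confidence level 95% (z = 1.96); population N = 285; the 0.5, read as a proportion p = 50%; n = 90; stated margin 8.56; drop-out at least 20%.

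**Formula.** Half-width for one proportion with finite-population correction:

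E = 1.96 × √(p(1−p)/n) × √((N−n)/(N−1))

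**Step 1: reproduce the stated figure (n = 90).**
- 1.96 × 0.5/√90 = 0.1033
- √((285−90)/284) = 0.8286
- E = 0.1033 × 0.8286 = 0.0856, or 8.56 percentage points.

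In the other direction, n₀ = 1.96² × 0.25/0.0856² = 131.07, and n = 131.07/(1 + 130.07/285) = 90.0. Without the population correction the half-width at 90 is 10.33, which does not match. So 8.56 uses all 90 patients, with none removed for drop-out.

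**Step 2: apply the protocol's drop-out.** 90 × (1 − 0.20) = 72, or 36 per arm. Because the text says at least 20%, 72 is a ceiling.
- 1.96 × 0.5/√72 = 0.1155
- √((285−72)/284) = 0.8660
- E = 0.1155 × 0.8660 = 0.1000, or 10.0 percentage points.

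| Drop-out | Evaluable | Margin (points) |
|---|---|---|
| 0% | 90 | 8.56 |
| 20% | 72 | 10.0 |
| 25% | 67.5 | 10.4 |
| 30% | 63 | 10.9 |

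**Step 3: could 90 already contain the allowance?** Setting E = 0.10 gives n₀ = 1.96² × 0.25/0.10² = 96.04 and n = 96.04/(1 + 95.04/285) = 72.02. Then 72/0.8 = 90 exactly. A plan that started from a margin of 10, found 72 and inflated for 20% loss would arrive at the protocol's number.

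**Step 4: a figure that bears on the two-arm comparison.** The protocol states no power, so 80% power and a two-sided 5% two-sample t-test are assumptions. With 36 per arm the normal approximation gives (1.96 + 0.842) × √(2/36) = 0.66 SD; the exact t-test calculation gives 0.67 SD. With 45 per arm and no drop-out, the t-test figure would be 0.60 SD.

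**The case against.** The strongest reply is that the missing table values may settle the matter. The drop-out sentence refers to the two tables, and the second calculator screen takes a sample size as input and returns an interval. A value as odd as 8.56 looks like the output of that screen with 90 entered, not like a chosen target. The first screen may well have shown 72 for a margin of 10, and 72/0.8 = 90. This part of the objection stands. A reader might infer that drop-out was forgotten and that 90/0.8 = 112.5, so 113 patients (114 for equal arms), should be enrolled. The document does not support that, because the arithmetic is fully consistent with a correct 20% allowance inside the 90.

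A second reply is that the protocol never says 8.56 applies at month 12; it attaches the figure to 90 patients, and for 90 it is correct. That is true as far as it goes. But it is the only precision given, it carries no such label, and the study's end points fall after the expected losses.

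A third reply concerns the 0.5. A reader might take it as a standardised difference and conclude that drop-out costs the study power against that target. The document does not support this either. The 8.56 reproduces with 0.5 as the calculator's percentage, a standardised difference of 0.5 does not lead to 45 per arm at 80% power (63 two-sided, 50 one-sided), and no power is claimed that could be lost.

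Finally, a margin for one pooled proportion would not describe a comparison of bile acids or microbiota between two arms even with no drop-out. This is correct. It limits what replacing 8.56 by 10.0 achieves, and it is why the fix adds a between-arm figure.

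**Conclusion.** The point holds in a limited form. Whichever way the 90 was reached, 8.56 is not the precision in the patients expected to reach 12 months. On the protocol's own formula and its own 20% loss, that precision is 10.0 percentage points at best. The difference is modest, about 1.4 points (10.0 − 8.56), and this is a self-described pilot. It is worth correcting because the remedy is free and the figure stands alone.

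The conclusion rests on reading 0.5 as p = 50% with N = 285 and a finite-population correction, which reproduces the stated value. The 0.67 SD rests on an assumed power and test and on 36 patients in each arm. Since "the enrollment in the two study groups will be on the basis of patient choice", equal arms are planned but not assured. It is not shown that drop-out was left out of the calculation or that enrolment is too small for the stated precision.

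**What to change.** In the Patients section:

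1. Keep 90 enrolled (45 per arm) and state that, with at least 20% drop-out, at most 72 (36 per arm) are expected to be evaluable at 12 months.
2. Replace 8.56 with 10.0, or keep 8.56 and label it as the precision for 90 patients with no drop-out. If the tables show a calculation from 72 to 90, say so in the text.
3. Add the between-arm difference detectable with 36 per arm: about 0.67 SD at 80% power with a two-sided 5% t-test, naming the power and the test as assumptions.

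The cost is wording only. There are no extra patients and no change to design or analysis; the stated precision becomes slightly less favourable.

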The biliopancreatic limb length may explain the results of superior excess weight reduction as well as the higher incidence of hemoglobin deficiency after 5 year follow-up comparing MGB vs RYGB (7). This malabsorption could result in severe malnutrition defined as a %EBMIL > 100 % and an albumin level < 30 g/l (8).

In 2005 Rutledge observed malnutrition in 31/2,401 patients (5), Noun et al. reported 4 cases of malnutrition out of 1,000 patients of MGB (9), Lee et al.

(10) reported a revision rate of 1.7% at 9 years follow-up in their series of 1,322 patients and the most common cause of revision was malnutrition in nine cases. In addition, Wang et al. (11) operated 423 MGB and reported anemia as a late complication in 28% of patients, and most cases were microcytic, the reason for the high incidence was reported to be likely due to the duodenal bypass with malabsorption of iron. However all data published on the mal-absorptive effects of MGB are retrospective so, until now, there is no prospective comparative study to assess the malabsorptive efficacy of MGB vs RYGB. Recently an experimental study carried out in a rat model evaluated the malabsorption of MGB versus RYGB suggesting a higher protein malabsorption induced by MGB (not compensated by the intestinal adaptation) than RYGB (12).

Recent works have indicated that the gut microbiota may mediate some of the beneficial effects of bariatric surgery, and changes in the composition and diversity of the gut microbiota have been observed in the short and long term after RYGB in humans (13, 14), as well as after vertical sleeve gastrectomy and RYGB in mice (15). However, there are no investigations of these changes after MGB.

AIM OF WORK:

To evaluate in patient undergoing MGB or RYGB the effect of the treatment on enteric mal-absorption and microbiota profile in the first year after surgery.

Primary end point:

-To evaluate and compare RYGB vs MGB bile acids levels and microbiota profile shift at 6 and 12 months after surgery and its impact on metabolic and nutritional status after surgery.

Secondary end point:

-To measure GLP-1 plasma level (pg/mL) before and 12 months after surgery in MGB vs RYGB patients.

Other parameters:

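### Conversion to an open operation and reoperation for complications are listed as exclusion criteria, so operated patients can be removed on events known only during or after surgery

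*Protocol*

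**What the plan says.** Under Inclusion Criteria, the protocol enrols "candidates to primary MGB or RYGB without any concomitant surgeries" apart from hiatal hernia repair, and states that "enrollment in the two study groups will be on the basis of patient choice". Eligibility and group are therefore settled before the operation.

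The Exclusion Criteria mix items known at screening (age, BMI, smoking, earlier surgery) with two that are not: "Conversion to open surgery" and "Postoperative complications requiring reoperation". A third, "No compliance to the follow up schedule", carries no time point.

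The aim is stated as "To evaluate in patient undergoing MGB or RYGB the effect of the treatment on enteric mal-absorption" and on the microbiota profile in the first year. The primary end point compares the two procedures on bile acids and microbiota at 6 and 12 months. The other parameters cover nutritional status and, in item 2, "To compare the effect of RYGB vs MGB surgery on total weight loss percent", co-morbidities and quality of life. One exclusion list governs all of them.

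Nothing in the protocol says that a converted or reoperated patient stays in follow-up or in the analysis. The 20% drop-out allowance under Patients does not say whether such patients count towards it.

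**The concern.** An eligibility rule should be one that can be applied to a candidate. Conversion is known only once surgery has begun, and reoperation only afterwards. Used as exclusions, they select patients on what happened during or after treatment. If the two procedures differ in how often these events occur, or in how far the affected patients' outcomes depart from the rest, the retained groups no longer give the contrast between the procedures. The result would also describe a subset that nobody can identify before operating.

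The link to outcome is plausible on the protocol's own account. Its background cites a series of 1,322 MGB patients with a 1.7% revision rate at 9 years, in which malnutrition was the most common cause of revision. Malabsorption and nutritional status are what this study measures, so excluding reoperated patients could remove cases of the effect under study.

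There is also a practical consequence. If sites stop assessing an excluded patient, the later meal tests, stool samples and blood tests do not exist, and no later analysis plan can recover them.

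**Working it through.** **When each item can be known**

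| Item in the exclusion list | Earliest time known | Applicable to a candidate? |
|---|---|---|
| Age, BMI, smoking, earlier surgery | Screening | Yes |
| Conversion | During surgery | No |
| Reoperation for a complication | After surgery | No |
| Non-compliance with follow-up | Screening if expected compliance is meant; months 6 to 12 if behaviour is meant | Depends on the reading |

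**Size of a possible shift**

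The protocol has no figure of its own to reproduce here, because it gives no 12-month rate of conversion or reoperation for either arm. The only input from the document is 45 patients per arm (Patients: "an effect size of 0.5, Sample size is 90 patients (45 MGB and 45 RYGB"). The rest is assumption.

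Let a proportion p of an arm be removed, with mean outcome d SD away from the retained patients' mean m.

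- All-patient mean = (1 − p)·m + p·(m + d) = m + p·d.
- Removal therefore shifts that arm's mean by p·d in absolute size.
- The between-arm comparison shifts by p₁·d₁ − p₂·d₂.

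With k of 45 removed from one arm and none from the other:

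| k | p = k/45 | Shift at d = 0.5 | Shift at d = 1 |
|---|---|---|---|
| 1 | 0.0222 | 0.011 SD | 0.022 SD |
| 2 | 0.0444 | 0.022 SD | 0.044 SD |
| 4 | 0.0889 | 0.044 SD | 0.089 SD |

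With removal in both arms and the same d in each:

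- 2% against 10%: 0.08 × 0.5 = 0.04 SD to 0.08 × 1 = 0.08 SD.
- 10% against 20%: 0.10 × 0.5 = 0.05 SD to 0.10 × 1 = 0.10 SD.
- Equal p and equal d: zero.

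**Scale**

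The standard error of a difference between two means with 45 per arm is √(1/45 + 1/45) = 0.211 SD. The largest one-arm shift in the table, 0.089 SD, is 0.089/0.211 = 0.42 of that.

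The cited revision rate of 1.7% corresponds to 0.017 × 45 = 0.77 patients, and at d = 1 to a shift of 0.017 SD. It is only a loose guide: it covers 9 years and MGB alone, late revision is not early reoperation, and conversion is not included.

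**The case against.** The best defence is that the restriction is deliberate. This is a pilot with bile-acid and microbiota end points and standardised techniques, and a reoperation could disturb those measures for reasons unrelated to the bypass. That stands as a reason to report the uncomplicated set. It does not justify an eligibility rule that also governs weight loss, nutrition, co-morbidities and quality of life.

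A second defence is that the bias is probably small. On the assumptions above that is fair: the one-arm shifts are under half a standard error. But the rule would still discard data that are already scheduled, and the document gives no ground for assuming equal event rates in the two arms.

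A third is that analysis sets belong in a statistical analysis plan, which is not shown. This is right about analysis sets, and their absence is not the complaint. The defect is that the protocol's own text places these events among the exclusions.

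Some stronger readings are tempting but unsupported:

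- **A large bias.** With 4 against 0 removals and d = 2, the shift is 0.0889 × 2 = 0.178 SD, or 36% of the protocol's effect size of 0.5 if that is in SD units. Nothing in the document supports that combination.
- **Non-compliance as a third exclusion of the same kind.** The line may be a screening judgement of expected compliance. The text does not say.
- **A contradiction between the 10% bowel tolerance and the expected 6–8 m bowel length.** No single reference length ±10% spans 6–8 m, but the line may refer to limb length: the RYGB biliopancreatic limb of 65–75 cm lies within 70 cm ± 10% (63–77 cm). The 6–8 m figure is also an expectation, not an eligibility range. What is fair to say is that no reference value is given.

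**Conclusion.** The point holds for conversion and reoperation. Both are listed as exclusions, neither can be known for a candidate, and nothing in the protocol keeps these patients in the study. Applied literally, the list can bias the comparison of procedures and narrows the population named in the aim.

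The direction and size of any bias cannot be determined from the document. The range of about 0.01 to 0.09 SD rests on assumed removals of 1 to 4 of 45 in one arm only and assumed differences of 0.5 to 1 SD. A reader might infer that the results will be biased, or biased in favour of one procedure. The document supports neither: the shift is zero if removal is equal and equally informative, and the background figure on malnutrition supports a mechanism, not a 12-month rate.

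Non-compliance is a matter for clarification. This should be fixed because the correction is cheap and data not collected cannot be recovered.

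**What to change.** 1. Take conversion and reoperation out of the Exclusion Criteria. Report both by arm, with the cause of each reoperation.
2. State that these patients continue with the scheduled 6- and 12-month assessments.
3. Make the main comparison on all enrolled patients who received MGB or RYGB, classified by the index procedure, so that a reoperation that alters the bypass does not move a patient between arms. Keep the uncomplicated set as a sensitivity analysis, notably for bile acids and microbiota.
4. Say whether the non-compliance item is a screening judgement. If it means behaviour during follow-up, treat it as drop-out and keep the data collected.
5. Reconcile the wording and role of two further lines that depend on information obtained after enrolment: the intraoperative bowel tolerance (Exclusion Criteria, with Intra-operatively) and the proton-pump-inhibitor condition tied to month 6, which does not make clear which status excludes or whether it is a sampling condition. No change to either clinical rule is proposed.

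The cost is a wording amendment, one extra analysis and slightly more outcome variability in the main set. The visits, meal tests and samples are already scheduled. Confounding from allocation by patient choice remains.

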- Free PPI 4 weeks before 6th month (after surgery)
- Corticosteroids, vitamin E, fish oil treatment in the previous two months
- Anti or pre- biotics treatment in the previous 2 months
- Chronic gastrointestinal diseases or syndromes (e.g., IBD, IBS)
- Previous bariatric surgery (intra-gastric balloon excluded).
- Previous resective bowel surgery

- Previous pancreatic surgery
- Previous hepato bilio pancreatic surgery
- Gallbladder gallstones

Methods:

Pre-and post-operative Assessment:

All patients will sign an informed consent (Sicob guidelines 2016). Study protocol will be approved by the Ethical Committee.

All patients will undergo routine blood laboratory investigations before surgery, 6 months and 12 months after surgery including: serum hemoglobin, glucose, HbA1c, cholesterol, triglycerides, LDL, HDL, T3, T4, TSH, GLP-1. Assessment of the nutritional status will be performed before 6- and 12 months after bariatric surgery by blood testing for serum iron, calcium, zinc and vitamins A, D, B12 and cortisol level.

A standardized meal test will be performed before, 6 and 12 months after bariatric surgery with 250 ml of liquid meal Oxepa®, (375 calories, 55.5% fat,

28% carbohydrate, 16.5% protein). Blood samples will be collected at baseline, 30, 60, 90 and 120 minutes after meal test in order to assess the concentration of the circulating lipids, GLP-1, bile acids (C4 precursor of bile acids) and FGF 19 (Fibroblast Growth Factor 19) levels. A stool sample will be collected at 0 – 6 – 12 months (It' s necessary to indicate date and time of defecation) stored at - 80°C for targeted gut microbiota metagenomic (MG) study, lipids and proteins levels assessment. Every sample will be made by two parts: one for metagenomics evaluation and the other one for lipids and proteins levels assessment. Before fecal sampling, patients will be asked to fill out a three days food diary. All patients with vitamin D deficiency (< 20 ng/mL) will be supplemented before surgery with 10,000 IU of Vitamin D daily (16). Every value of nutritional status should be annotated in Winfood software. The selection criteria, work up, informed consent and schedule of the multidisciplinary follow up will follow the Guidelines of Italian Society for Obesity Surgery (SICOB) adopted in September 2016 (www.sicob.org).

Intra-operatively:

Standardization of the techniques will be guaranteed:

1. RYGB group
2. MGB group

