All patients will have intraoperative measurement of the whole length of bowel from Treitz ligament to the ileocecal junction (expected range 6-8 m). The common limb will be therefore about 2/3 of total small bowel length.

Roux en Y gastric bypass

The steps of the standard double loop RYGB technique will be followed (17). The gastric pouch will be created 7 cm from the gastro-esophageal junction to obtain a volume of 30-40 ml, and the length of the alimentary limb will be 150 cm and 3.5-4 cm gastro-jejunostomy will be performed by linear stapler. The length of the biliopancreatic limb will be from 65 to 75 cm beyond the ligament of Treitz. The lengths of both limbs should carefully measured with a graduated instrument. The mesenteric defects will be closed.

Mini-gastric Bypass

The gastric pouch will be performed starting below the incisura angularis (transverse resection 4 cm) on the lesser curvature (18). Then the stomach will be transected against a 36 Fr bougie up to the gastro-esophageal junction. Then 1/3 of the small bowel will be excluded (approximately 200cms) and 3.5-4 cm gastro-jejunostomy will be performed by linear stapler.

Postoperative diet

After surgery and under the supervision of the registered dietitian, the diet will be transitioned from liquid diet for 2 weeks to pureed proteic diet for 1 week then soft solid proteic diet for 2 weeks then maintenance (regular food). All patients should have daily vitamin and mineral supplementation up one year after surgery following the chart below:

Vitamin A	0,8 mg
Vitamin B	11,65 mg
Vitamin B	22,1 mg
Vitamin B	324 mg
Vitamin B	62,1 mg
Vitamin B12	0,00375 mg
Vitamin C	120 mg
Vitamin D3	0,0075 mg
Vitamin E	12 mg
Vitamin K1	0,0375 mg
Folic Acid	0,2 mg
Pantothenic Acid	9 mg
Iron	21 mg
Magnesium	187,5 mg
Selenium	0,055 mg
Zinc	10 mg

Diet progression after bariatric surgery

1. Liquid Proteic Diet (for 2 weeks)

Types of food	Calories/day
Reduced fat milk Lactose-free: 200ml	Protein: 52.32g (31.29%)

Fruit juice: 200ml	Fat: 14.52g (19.54%)
Light white yogurt: 125ml	Carbohydrate: 86.6g (51.58%)
Vegetable clear broth: 400ml	Kcal: 669
Oral protein supplementation: 400ml	

2. Pureed Proteic Diet (for 1 week)

Types of food	Calories/day
Reduced fat milk Lactose-free: 200ml	Protein: 62.4g (25.69%)
Light white yogurt: 125ml	Fat: 43.26g (40.07%)
Vegetable clear broth: 400ml	Carbohydrate: 85.52g (35.21%)
Oral protein supplementation: 400ml	Kcal: 971.65

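### The only PPI rule names month 6, so the baseline stool sample behind the microbiota shift has no PPI rule, and the later samples have no clear antibiotic rule

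*Protocol*

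**What the plan says.** The Primary end point section asks for a comparison of the two operations on "bile acids levels and microbiota profile shift at 6 and 12 months after surgery". The section Pre-and post-operative Assessment sets the sampling times: "A stool sample will be collected at 0 – 6 – 12 months". Its instructions around sampling cover the date and time of defecation, frozen storage and diet: "Before fecal sampling, patients will be asked to fill out a three days food diary". It sets no drug condition before any sample.

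The drug rules stand in the Exclusion Criteria:

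- PPI: "Free PPI 4 weeks before 6th month (after surgery"). This is the only mention of PPI in the protocol.
- Antibiotics and prebiotics: "Anti or pre- biotics treatment in the previous 2 months".
- Other agents: "Corticosteroids, vitamin E, fish oil treatment in the previous two months".

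The last two items do not say which date the window precedes. The same list also holds items that can only be judged at or after surgery, such as conversion to open surgery and reoperation for complications. Under Inclusion Criteria, the patient chooses the operation. Under Data recording and variables analysis, the study records "detailed information on history, preoperative data, surgical procedure, intra-operative findings, and postoperative course"; drugs are not named there.

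**The concern.** A shift is a difference between a follow-up sample and a baseline sample, so the two should be taken under the same conditions. The protocol restricts PPI, antibiotics and prebiotics, so it treats them as worth controlling. Yet the PPI restriction names one of the three sampling times, and the antibiotic window is not tied to any sample.

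If some patients take PPI at baseline and all are off PPI for four weeks before month 6, part of the change within an arm could come from stopping the drug and be read as an effect of surgery. The arms are not randomised, so nothing in the design balances PPI or antibiotic use between them. If exposure before each sample is not recorded, it may be hard to separate the two effects later.

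The PPI line also works badly as an instruction. In an exclusion list it reads as excluding patients who are PPI-free, which is probably a drafting slip for a wash-out. In addition, a condition at month 6 cannot be checked at enrolment.

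**Working it through.** There is no stated figure to reproduce. The check sets the drug rules against the three stool samples, with the PPI line taken as a wash-out.

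**Inputs.** Stool at months 0, 6 and 12 (Pre-and post-operative Assessment). PPI-free for 4 weeks before month 6 (Exclusion Criteria). No antibiotics or prebiotics in a 2-month window without a stated reference date (Exclusion Criteria).

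**Readings.** The PPI line can mean (a) a wash-out before month 6 only, or (b) PPI-free from about month 5 onward. The antibiotic window can be dated (i) from enrolment, assuming that the month-0 sample is taken close to enrolment, or (ii) from each sample.

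| PPI reading | Antibiotic reading | Month 0 | Month 6 | Month 12 | Samples with both rules |
|---|---|---|---|---|---|
| (a) month 6 only | (i) enrolment | antibiotic | PPI | none | 0 of 3 |
| (a) month 6 only | (ii) per sample | antibiotic | both | antibiotic | 1 of 3 |
| (b) from month 5 | (i) enrolment | antibiotic | PPI | PPI | 0 of 3 |
| (b) from month 5 | (ii) per sample | antibiotic | both | both | 2 of 3 |

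**Counts over the four rows.**

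- Month 0 has no PPI rule: 4 of 4.
- Month 12 has no PPI rule: 2 of 4, namely both rows with reading (a).
- The rules differ between months 0 and 6: 4 of 4.
- The rules differ between months 0 and 12: 3 of 4. The exception is (a) with (ii).
- All three samples carry both rules: 0 of 4.

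**Which antibiotic reading is more natural.** A look-back window in an eligibility list is ordinarily counted from enrolment. The vitamin E item points the same way: its window is worded in parallel, while under Postoperative diet "All patients should have daily vitamin and mineral supplementation up one year after surgery", and that supplement contains 12 mg of vitamin E. This supports reading (i) but does not prove it, since a routine multivitamin need not count as vitamin E treatment. The post-surgical items in the same list keep reading (ii) possible.

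**Size.** The document gives no PPI, antibiotic or prebiotic use at any visit or in either arm, so no bias can be calculated.

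**The case against.** Several points on the other side have force.

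- **Month 12.** A reader might infer that months 0 and 12 both lack a PPI rule whatever the reading. The text does not support that: if patients stop PPI about four weeks before month 6 and stay off, month 12 is covered. Only the month-0 gap survives every reading.
- **Bias between arms.** A reader might infer that the comparison of the two operations is biased. Each rule applies equally to both arms at each visit, so a PPI effect within an arm distorts the contrast only if PPI use, or its effect, differs by arm. The document shows neither, nor does it say that any patient takes PPI at baseline. This objection stands: what remains is a risk.
- **Missing antibiotic date.** Taken alone this is a wording gap and not a contradiction, because dating from enrolment is ordinary. What remains is that, on that reading, no antibiotic rule applies after surgery.
- **Purpose of the PPI line.** The protocol does not say that it concerns stool. The month-6 visit also includes the meal test with bile acids and gut hormones. But the meal test too is done before surgery and at 6 and 12 months, so that purpose leaves the same mismatch. Whatever the purpose, the month-6 stool sample is taken under a condition that the baseline sample is not.
- **Recording.** Medical history and postoperative course may include drugs, and the case report form is not shown. It would go too far to say that exposure will be lost. The protocol only fails to require it for each sample.
- **Pilot status.** Little can be quantified and the study is a pilot, which limits the weight of the point. It does not remove it, because conditions before sampling are a protocol matter and later analysis cannot restore exposure that was not recorded.

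**Conclusion.** The point holds in a limited form. The only PPI rule is inverted by its place in the exclusion list and names month 6 alone. The baseline stool sample has no PPI rule on any reading, and the month-12 sample has none on the plainer of the two readings. With the antibiotic window dated from enrolment, the 6- and 12-month samples have no antibiotic rule.

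Followed as written, the plan compares a month-0 sample with a month-6 sample taken under different stated drug conditions in all four combinations of readings. Part of the 0-to-6-month shift may thus reflect a change in PPI use, and exposure may differ between patient-chosen arms. How much depends on actual drug use, which the document does not give. The point concerns the microbiota part of the primary end point; no effect on the bile acid part is claimed. The protocol should be corrected, but no bias has been shown.

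**What to change.** 1. Take the PPI item out of the Exclusion Criteria and replace it with one pre-sampling rule for months 0, 6 and 12: no PPI for 4 weeks where clinically acceptable, and no antibiotics or prebiotics for 2 months.
2. Keep the antibiotic, prebiotic, corticosteroid, vitamin E and fish oil items as enrolment criteria, and state that their windows count back from enrolment.
3. Record PPI, antibiotic and prebiotic exposure before each stool sample, beside the food diary.
4. Keep exposed patients in the study, flag their samples, and report a sensitivity analysis without the flagged samples. Interpret it with care: post-operative PPI use may itself result from the operation, since the protocol compares bile-reflux lesions between the arms, so removing these samples could introduce a selection of its own.

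**Cost.** One medication field at three existing visits, one extra analysis, some flagged samples, and a short PPI interruption before months 0 and 12 for patients who can tolerate it. The interruption is a real clinical burden, so patients who need PPI should continue it and have the sample flagged.
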